6.3.3. Food and Beverage Restrictions

Subjects must come for the study visits, during the treatment and FU period, in the morning. At baseline (Visit 1), Day 15 (Visit 3), and Day 43 (Visit 5) and if applicable the ED visit, subjects need to come for the study visits in a fasting state (no food intake for at least 8 hours).

Subjects will refrain from the consumption of grapefruit juice, grapefruit or Seville oranges beginning 48 hours prior to administration of the initial dose of IP, throughout the study until 7 days after the last IP administration.

6.4. Treatment Discontinuation (Temporarily and Permanently), Subject Withdrawal and Study Termination

A subject may be withdrawn from the clinical study at any time without the subject's consent if the investigator or sponsor determines that it is not in the best interest of the subject to continue participation. In such case, the reason for withdrawal will be documented in the source documents, and the subject will be asked to complete the ED visit and FU visit for safety assessments.

Treatment with IP should be discontinued by the investigator (who may consult the sponsor's medical leader) for any of the following conditions:

- Life-threatening adverse event (AE) or an SAE that places the subject at immediate risk.
- Serious infections deemed related to study treatment by the investigator, and requiring parenteral antimicrobial therapy and/or hospitalization.
- Confirmed pregnancy or lactation.
- Arrhythmia or conduction abnormality, including but not limited to prolonged QTcF, where the severity is categorized as Common Terminology Criteria for Adverse Events (CTCAE) Grade 3 or higher (QTc >500 ms on at least 2 separate ECGs), or clinically significant arrhythmia from any grade.
- Liver enzyme increase (see also [Appendix 9](#))
 - AST and/or ALT ≥ 8 x the ULN.
 - AST and/or ALT elevations ≥ 3 x ULN with signs of liver damage (i.e., with the appearance of fatigue, nausea, vomiting, right upper quadrant pain or tenderness, fever, rash and/or eosinophilia [$>5\%$], and/or total bilirubin ≥ 2.0 x ULN or international normalized ratio [INR] >1.5)
 - In addition, a dose interruption or reduction (if applicable) should be considered if AST and/or ALT ≥ 3 x ULN and <5 x ULN and dosing with IP should be interrupted if AST and/or ALT ≥ 5 and <8 x ULN.

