- Subjects presenting with signs and symptoms of SARS-CoV-2 infection should immediately contact the site investigator, who should inform the sponsor's medical responsible as soon as possible, and report an AE/SAE as applicable. In case of suspected SARS-CoV-2 infection RT-PCR and serology tests should be performed to confirm the infection. The investigator, preferably after consultation with the sponsor's medical responsible, must discontinue the subject from the study. The subject could be tested for SARS-CoV-2 in facilities outside the study site and if so, the subject should be instructed to immediately inform the study investigator if the test is positive and test results should be shared with the investigator as soon as possible.

For subjects having:

- AST or ALT ≥ 8 xULN
- AST or ALT ≥ 3 xULN with signs of liver damage (i.e. with the appearance of fatigue, nausea, vomiting, right upper quadrant pain or tenderness, fever, rash and/or eosinophilia [$>5\%$], and/or total bilirubin ≥ 1.5 xULN or INR >1.5)

The following steps will need to be performed by the investigator:

- The site should immediately contact the subject and require the subject to discontinue IP immediately. The subject should be asked to return to the site within a 48-hour window from awareness of the result.
- A full evaluation of various causes of hepatitis should be conducted (i.e., infectious, alcohol, medications, anatomical).

- An assessment of other concomitant medications and SoC should be made. The investigator should consider whether it is in the best interest of the subject to stop/interrupt concomitant medications and SoC treatment.
- A detailed history including relevant information on alcohol use, recreational drug use, supplement consumption, any herbal remedies, family history, sexual history, travel history, history of contact with a jaundiced subject, surgery, occupational history, blood transfusion, history of liver or allergic disease, and any other potential causes of attributable to a liver insult should be collected.
- A detailed assessment of the subject's clinical condition and repeat laboratory tests for liver function tests (LFTs), including albumin, creatine kinase, total bilirubin (direct and indirect), gamma glutamyl transferase (GGT), INR and alkaline phosphatase should be done.

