- Further testing for hepatitis A, B, and C, and for autoimmune hepatitis should be done. Other causes of viral hepatitis (cytomegalovirus or Epstein Barr virus etc) should be excluded. Liver imaging should be considered.
- Referral to a hepatologist or gastroenterologist should be requested.
- All these cases should be reported as SAEs.

Every effort should be made to keep subjects in the study and on treatment. However, the investigator, who may consult the sponsor's medical leader, can consider stopping the study treatment in case of concerns about the subject's safety, serious or severe AEs or worsening of the disease condition, which in the investigator's opinion needs an alternative treatment approach not being covered in the clinical study (e.g., rescue medication). If IP treatment is interrupted due to an SAE, IP could be restarted, as per the investigator's judgement and after consultation with the sponsor medical leader.

When study treatment is discontinued, the subject will be requested to complete the assessments for the ED visit and return for the FU visit. Reason for discontinuation must be documented in the case report form (CRF).

Subjects will be informed prior to clinical study entry that they are allowed to withdraw from the clinical study. At any time and for any reason, a subject's participation in the clinical study may terminate at their request, without prejudice to their future medical care. The subject will be encouraged to share the reason(s) for withdrawal so this can be documented in the source documents, and to complete the ED Visit and follow-up visit for safety assessments, but will not be obliged to do so.

Subjects who withdraw from the clinical study without contact with the site (lost-to-follow-up) should be contacted by the site so that their health status can be assessed and documented in the source documents. The site should make every effort to understand whether the subject is alive, including checking the medical records and contacting general practitioner or relatives, if necessary. All attempts must be documented in the source documents.

The sponsor has the right to terminate the clinical study at any time and for any reason. In this event, the investigator(s) and relevant authorities will be informed of the reason for clinical study termination.

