11.1.4. Adverse Events of Special Interest

Not applicable.

11.1.5. Clinical Laboratory Abnormalities and Other Abnormal Assessments as Adverse Events or Serious Adverse Events

Laboratory abnormalities without clinical significance based on the investigator's judgment are not considered AEs or SAEs. However, laboratory abnormalities (e.g. clinical chemistry, hematology, and urinalysis) or other abnormal (clinical study-specific) assessments (e.g. ECG, radiography, vital signs) that require medical or surgical intervention, are associated with signs and/or symptoms, and/or lead to IP interruption, modification or discontinuation must be recorded as an AE or SAE if they meet the definition as described in Sections 11.1.1 and 11.1.2, respectively. If the laboratory abnormality is part of a syndrome, the syndrome or diagnosis is to be reported (e.g. anemia instead of decreased hemoglobin).

The following liver enzyme elevations should be reported as SAEs:

- AST or ALT \geq 8xULN.
- AST or ALT \geq 3xULN with signs of liver damage (total bilirubin $>$ 2xULN OR international normalized ratio $>$ 1.5, and/or with the appearance of fatigue, nausea, vomiting, right upper quadrant pain or tenderness, fever, rash and/or eosinophilia [$>$ 5%]).

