Appendix 9: Algorithm for Elevated Liver Function Tests

| | AST or ALT increase to | | | | |
|------------------------|---|---|---|---|-----------------------------|
| Value Range | $\geq 1.5x$ to $3x$ ULN | $\geq 3x$ to $<5x$ ULN | $\geq 5x$ to $<8x$ ULN | $\geq 3x$ ULN with signs of liver damage ¹ | $\geq 8x$ ULN |
| IP Action | Continue as planned | Reduce or interrupt IP for at least 2 weeks | Interrupt IP for at least 2 weeks Close observation ² | Discontinue IP ² | Discontinue IP ² |
| | | | | | |
| After at least 2 weeks | AST and ALT $<3x$ ULN | AST or ALT $\geq 3x$ ULN | | | |
| | Weekly LFTs for the first 2 weeks (biweekly for the following weeks, or more frequently at investigator's discretion) | Discontinue IP Report SAE and complete liver event page for any of abnormalities listed below ³ : 
 - AST/ALT increase $\geq 8x$ULN - AST/ALT increase $\geq 3x$ULN with signs of liver damage¹ | | | |

¹ Signs of liver damage:

- total bilirubin $\geq 2.0x$ ULN OR international normalized ratio >1.5 , and/or
- symptoms: appearance of fatigue, nausea, vomiting, right upper abdominal quadrant pain or tenderness, fever, rash and/or eosinophilia ($>5\%$)

² Close observation recommendations:

- Monitor 2 to 3 times per week all of the following parameters: ALT, AST, alkaline phosphatase, total bilirubin, eosinophils, INR. If local regulations allow, home visits can be performed if subjects cannot come to the clinical study center.
- Frequency of retesting can be reduced to once a week or less if abnormalities stabilize or the IP has been discontinued; however, monitoring might still be needed more frequently taking into consideration the standard of care and/or changes to this.
- Based upon investigator's discretion gastroenterology or hepatology consultations, additional serology testing, imaging and pathology assessments may be required.
- Re-query history of symptoms, prior and concurrent diseases, concomitant medication and non-prescription medicines, herbal, dietary supplements, alcohol use, recreational drug use, special diets.
- Rule out all of the following: acute viral hepatitis, autoimmune hepatitis, alcoholic hepatitis, non-alcoholic fatty hepatitis, hypoxic/ischemic hepatitis, biliary tract disease, and cholestasis.
- Re-query exposure to environmental chemical agents.

³ The following steps should be followed:

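### Section 6.4 sets two bilirubin limits for the liver stopping rule (2.0x and 1.5x ULN), so the same results can require an immediate stop and an SAE report under one text and not under the others

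*Protocol*

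**What the plan says.** Four places in the protocol set liver rules.

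- **Section 6.4, discontinuation list.** IP stops at AST or ALT of 8x ULN or more, or at 3x or more with signs of liver damage. The laboratory limb of those signs reads "and/or total bilirubin ≥ 2.0 x ULN or international normalized ratio [INR] >1.5". Below that, at 3x to <5x ULN, "a dose interruption or reduction (if applicable) should be considered". At 5x to <8x, "dosing with IP should be interrupted if AST and/or ALT" falls in that range. No duration is given for either band. The bullet refers the reader to Appendix 9.
- **Section 6.4, list of steps for the investigator.** This has the same two triggers, but the laboratory limb now reads "and/or total bilirubin ≥ 1.5 xULN or INR >1.5". The site must "require the subject to discontinue IP immediately", and the list ends with "All these cases should be reported as SAEs".
- **Section 11.1.5, liver elevations to be reported as SAEs.** AST or ALT of 3x or more counts "with signs of liver damage (total bilirubin $>$ 2xULN OR international normalized ratio" above 1.5, or with the listed symptoms or eosinophilia.
- **Appendix 9.** At 3x to <5x: "Reduce or interrupt IP for at least 2 weeks". At 5x to <8x: interrupt for at least 2 weeks, with close observation. The footnote on signs of liver damage puts bilirubin at 2.0x ULN or more.

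**The concern.** A liver stopping rule should give one answer for one set of results. Here the bilirubin limit decides whether a subject comes off drug at once and whether the site owes an SAE report, which 11.3.2 requires within 24 hours. Two limits appear inside the same section, and reading further does not settle which governs. Sites could act differently on identical results. Counts of serious TEAEs and of TEAEs leading to discontinuation, both tabulated under SAP 6.3.1.8, would then depend partly on which list a site followed.

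Section 5.5 describes this as the first study of the compound in subjects with moderately to severely active UC. Inclusion criterion 13g also admits documented Gilbert's disease with bilirubin above 1.5x ULN. Such a subject can meet the lower bilirubin limit from the day of entry, so any later AST or ALT of 3x or more would trigger the stop.

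The second, smaller issue is the difference in force between 6.4 and Appendix 9 at 3x to <5x ULN.

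**Working it through.** No power or sample-size figure is involved. The check is a comparison of texts over a grid.

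**Inputs.** AST/ALT bands (3x to <5x, 5x to <8x, 8x or more) come from 6.4 and Appendix 9. Bilirubin bands (<1.5x, 1.5x to <2.0x, 2.0x or more) come from the two definitions in 6.4. Assume INR of 1.5 or less, no listed symptoms and no eosinophilia, so that only bilirubin can supply the sign of liver damage.

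| AST/ALT | Bilirubin | 6.4 discontinuation list | 6.4 steps list | Appendix 9 | SAE under 11.1.5 |
|---|---|---|---|---|---|
| 3x to <5x | <1.5x | consider action | not triggered | reduce or interrupt, 2 weeks or more | no |
| 3x to <5x | 1.5x to <2.0x | consider action | **stop, SAE** | reduce or interrupt, 2 weeks or more; no SAE | no |
| 3x to <5x | 2.0x or more | stop | stop, SAE | stop, SAE | yes |
| 5x to <8x | <1.5x | interrupt | not triggered | interrupt, 2 weeks or more | no |
| 5x to <8x | 1.5x to <2.0x | interrupt | **stop, SAE** | interrupt, 2 weeks or more; no SAE | no |
| 5x to <8x | 2.0x or more | stop | stop, SAE | stop, SAE | yes |
| 8x or more | any (3 cells) | stop | stop, SAE | stop, SAE | yes |

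The 11.1.5 limit is strictly above 2x, so it departs from the other 2.0x texts only at exactly 2.0x.

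**Count.**
- 2 cells conflict on both stopping and SAE reporting (bilirubin 1.5x to <2.0x, AST/ALT below 8x). No reading satisfies all four texts.
- 1 cell differs in force (3x to <5x, bilirubin <1.5x): discretionary in 6.4, directed in Appendix 9. A site that follows Appendix 9 also complies with 6.4.
- 1 cell is an omission (5x to <8x, bilirubin <1.5x): both texts interrupt, and Appendix 9 supplies the duration and follow-up.
- 5 cells agree on IP action. 2 + 1 + 1 + 5 = 9.

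**Whether "reduce" can be carried out.** Section 5.1 gives one dose level, 400 mg once daily. Section 7.2 requires the whole reconstituted solution to be taken. The action-taken list in 11.2.1 has no entry for a reduced dose. Reduction is therefore named but has no procedure, and in practice Appendix 9 means interruption.

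**Gilbert's disease.** Criterion 13g caps bilirubin at 1.5x ULN except in documented Gilbert's disease, where it gives no upper limit. Such a subject may enter above 1.5x or above 2.0x, so the baseline problem exists under either limit.

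**The case against.** The best reply is that much of this is already covered. Section 6.4 points to Appendix 9, and a site that uses the appendix satisfies the dose-action sentence in 6.4. That stands for both bands when bilirubin is below 1.5x. It does not help with the bilirubin limit, because the conflicting list is itself in 6.4 and its instruction to stop is not conditional on Appendix 9.

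Safeguards also exist: laboratory alerts for Grade 3 and above (5.5), unblinded safety review (10.1), and the investigator's freedom to stop IP for safety (6.4). These limit the harm but do not say which threshold applies. Section 5.5 names no grading scale for the alerts. If the SAP Appendix I scale is used, Grade 3 for AST/ALT starts above 5x, and enzyme values in the 3x to <5x band would raise no alert.

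SAP 6.3.2.8 tabulates AST/ALT above 3x with bilirubin above 1.5x as well as above 2x. Both levels interest the sponsor, so the SAP does not show which of the two is the slip.

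A reader might infer more than the text supports:

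- **That four of nine cells conflict, with three different actions at 5x to <8x.** Two of those four cells are compatible, and at 5x to <8x the discontinuation list and Appendix 9 both interrupt.
- **That Appendix 9 costs 14 of 42 treatment days (33%).** On-treatment safety bloods after Day 1 are scheduled on Days 15, 29 and 43. A rise found on Day 43 costs essentially nothing, and one found on Day 29 leaves at most 43 - 29 = 14 days. On scheduled tests, only a Day 15 finding leaves dosing time after a 2-week pause (28 - 14 = 14 days).
- **That Appendix 9 plainly orders a stop if values are still 3x or more after 2 weeks.** That is the natural reading, but the table's columns are broken in the text available, so the point does not rest on it.

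**Conclusion.** The inconsistency is real and should be corrected. For AST or ALT from 3x to <8x ULN with bilirubin from 1.5x to <2.0x, INR of 1.5 or less, and no symptoms or eosinophilia, one part of 6.4 requires an immediate stop and an SAE report. The other part of 6.4, Appendix 9 and 11.1.5 do not. This is 2 of 9 grid cells, and it holds for a site that has read every page. The thresholds are legible running text in protocol version 1.0, which SAP version 3.0 still cites as its basis, so neither redaction nor an amendment log explains them.

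The mismatch at 3x to <5x is secondary: a discretionary instruction against a directed one. At 5x to <8x, 6.4 merely omits detail.

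The documents give no expected rate of AST or ALT at 3x ULN or more. Entry requires 1.5x ULN or less, so few of the 30 subjects are likely to be affected. A reader might infer a threat to the primary comparison; nothing in the documents supports that. The case rests on subject safety and consistent conduct.

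**What to change.** 1. Have the sponsor's medical team choose one bilirubin limit and use it, with the same inequality sign, in both lists of 6.4, in 11.1.5 and in the Appendix 9 footnote. Three of the four already sit at about 2x, so that is the smaller edit; 1.5x is the more cautious choice. The lower limit should not be dropped by default without a recorded medical decision.
2. State how documented Gilbert's disease admitted under criterion 13g is handled. This is needed under either limit.
3. In 6.4, replace the action wording for AST/ALT from 3x to <8x ULN without signs of liver damage with an instruction to follow Appendix 9.
4. Delete dose reduction from 6.4 and Appendix 9, since there is one 400 mg dose and no reduced-dose procedure.

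The cost is wording in four places, by amendment or clarification letter, with no new procedure. Item 3 removes some investigator discretion at 3x to <5x, so a few subjects may lose exposure. With 1.5x there may be a few more discontinuations and SAE reports. With 2.0x, subjects between 1.5x and 2.0x are interrupted rather than stopped at once, and the investigator keeps the freedom to stop.

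### The bilirubin limit that makes AST/ALT ≥3x ULN a stop-IP and SAE case is printed in three forms, and Section 6.4 and Appendix 9 also differ on the action at 3x to <5x ULN

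*Protocol*

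**What the plan says.** Four places in the protocol define when AST or ALT ≥3x ULN counts as a case with signs of liver injury. Besides bilirubin, each lists INR >1.5, certain symptoms and eosinophils >5%.

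- **Section 6.4, stopping list.** IP is discontinued at AST/ALT ≥8x ULN, or at ≥3x with "total bilirubin ≥ 2.0 x ULN or international normalized ratio [INR" or another listed sign. Without such signs, at 3x to <5x, "a dose interruption or reduction (if applicable) should be considered"; at 5x to <8x, IP should be interrupted. The list points the reader to Appendix 9.
- **Section 6.4, investigator steps.** The bilirubin limit here is "and/or total bilirubin ≥ 1.5 xULN or INR >1.5". The site must "require the subject to discontinue IP immediately" and have the subject back within 48 hours. The last step reads "All these cases should be reported as SAEs".
- **Section 11.1.5, SAE rule.** SAE reporting applies at AST/ALT ≥8x, or ≥3x with "signs of liver damage (total bilirubin $>$ 2xULN OR international normalized ratio" above 1.5 or another sign. This section sets no IP action.
- **Appendix 9.** Footnote 1 uses "total bilirubin $\geq 2.0x$ ULN OR international normalized ratio" above 1.5. Such cases are to be discontinued and reported as SAEs. In the 3x to <5x column without signs, the action is "Reduce or interrupt IP for at least 2 weeks".

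**The concern.** A combined rise in transaminases and bilirubin is a central liver stopping signal, and Section 5.5 says this is the first study of GLPG3970 in subjects with UC. If the trigger depends on which page a site consults, the same result can lead to different IP handling and a different SAE decision. The SAE decision also starts the 24-hour reporting duty in Section 11.3.2.

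There is a smaller consequence for efficacy. SAP Section 3 handles early treatment discontinuation by a hypothetical strategy and other intercurrent events by treatment policy. SAP Table 3 excludes Week 6 assessments made more than 2 days after the last dose (7 days for endoscopy), and SAP Section 6.2.2.2 imputes a missing Week 6 MCS. A subject who stops for good around Day 15 would therefore have the primary endpoint imputed, whereas one who pauses and resumes could contribute observed data.

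**Working it through.** There is no figure in the plan to reproduce. The check applies the printed rules to specific results, in multiples of ULN. It assumes no listed symptom, eosinophils ≤5% and INR ≤1.5; with AST/ALT ≥3x, any one of those signs would make all three IP rules say discontinue.

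| AST/ALT; bilirubin | 6.4 stopping list | 6.4 investigator steps | Appendix 9 | 11.1.5 |
|---|---|---|---|---|
| 4; 1.0 | consider interruption or reduction | not triggered | reduce or interrupt | limit not met |
| 4; 1.7 | consider interruption or reduction | discontinue + SAE | reduce or interrupt | limit not met |
| 4; 2.0 | discontinue | discontinue + SAE | discontinue + SAE | limit not met |
| 4; 2.1 | discontinue | discontinue + SAE | discontinue + SAE | SAE |
| 6; 1.7 | interrupt | discontinue + SAE | interrupt | limit not met |
| 8; 1.0 | discontinue | discontinue + SAE | discontinue + SAE | SAE |

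Limit not met means only that the liver rule in Section 11.1.5 does not apply; the general SAE criteria in Section 11.1.2 still could.

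Three separate differences follow.

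1. **1.5x against 2.0x.** For AST/ALT ≥3x to <8x and bilirubin ≥1.5x to <2.0x, the investigator steps say discontinue and report. The stopping list and Appendix 9 do not reach discontinuation.
2. **≥2.0x against >2x.** This matters only at exactly 2.0x. All three IP rules then say discontinue, and both the investigator steps and Appendix 9 call for an SAE report, but the Section 11.1.5 limit is not met. Between the investigator steps and Section 11.1.5, the SAE conflict covers bilirubin 1.5x to 2.0x inclusive.
3. **Action wording at 3x to <5x.** The first row shows this difference with bilirubin at 1.0x, so it does not come from the bilirubin limits. The 2-week minimum in Appendix 9 is 2/6, or one third, of the treatment period. Reduction has no defined meaning here: Section 5.1 gives one dose level (400 mg once daily), Section 7.2 requires the whole solution to be drunk, and the action list in Section 11.2.1 offers unchanged, temporarily or permanently discontinued, or not applicable.

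Outside these ranges, with AST/ALT ≥8x, or ≥3x with bilirubin above 2.0x, the IP rules agree on discontinuation and the SAE rules agree on reporting.

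The SAP does not indicate which limit is meant. Section 6.3.2.8 tabulates AST/ALT >3x with bilirubin at both >1.5x and >2x ULN.

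On scale, one subject is 1/20 = 5% of the planned GLPG3970 arm or 1/10 = 10% of placebo.

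**The case against.** The best defence is that the rules can all be obeyed together. The investigator steps are mandatory and sit in the same section as the stopping list. Asking a site to consider a pause does not forbid stopping, and Section 11.1.5 says what must be reported without excluding anything else. A site that applies all of Section 6.4 would discontinue IP and report an SAE at bilirubin 1.7x without breaching any other section. The stopping list also refers to Appendix 9, so the two can be read as general text and its detailed algorithm.

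Part of this stands: the strictest reading is feasible, and the exact-2.0x mismatch is narrow. But no precedence rule is written. Appendix 9 attaches essentially the same procedure (immediate discontinuation, 48-hour return, work-up, SAE report) to ≥2.0x, so the lower limit cannot be explained as a deliberately broader work-up trigger. Section 6.4 also asks that every effort be made to keep subjects on treatment, which pulls against always taking the strictest rule.

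A reader might infer more than the text supports:

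- **Three limits produce three IP actions.** They do not. Section 11.1.5 sets no IP action, and the stopping list and Appendix 9 share the same limit. The third action comes from the separate wording difference at 3x to <5x.
- **The investigator steps end treatment permanently.** They require immediate discontinuation but do not say permanent. Section 6.4 covers both kinds of discontinuation and allows a restart after an interruption for an SAE.
- **The Grade 3 laboratory alert in Section 5.5 misses AST/ALT of 3x to 5x.** That needs the grades in SAP Appendix I. The protocol names CTCAE for laboratory grading (Section 9.3.5.3) and AE severity (Section 11.2.3), and its cut-offs are not printed, so no gap is shown.
- **A permitted entry bilirubin could trigger the ≥1.5x rule.** Inclusion criterion 13 also caps AST and ALT at 1.5x ULN, so an entry result cannot meet the combined rule.

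**Conclusion.** The inconsistency is real. One discontinuation and SAE procedure carries two bilirubin triggers, and the SAE section uses a third form. The main conflict covers AST/ALT ≥3x to <8x with bilirubin ≥1.5x to <2.0x ULN and no other sign; a second, SAE-only conflict sits at exactly 2.0x. The difference in action at 3x to <5x is a separate drafting fault. The conclusion rests on the printed protocol text alone, and the documents give no basis for estimating how many subjects would fall in these ranges. It should be corrected because it concerns a safety stopping rule and the correction is cheap.

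**What to change.** 1. **Bilirubin limit.** Use one limit with the same inequality sign in both lists of Section 6.4, in Section 11.1.5 and in Appendix 9. The sponsor's medical lead should choose it. Taking ≥1.5x ULN keeps the stricter trigger and means editing the stopping list, Section 11.1.5 and Appendix 9. Taking ≥2.0x ULN means editing only the investigator steps and Section 11.1.5, but it relaxes the trigger in the investigator steps.
2. **Action at 3x to <5x ULN without other signs.** Give the Section 6.4 stopping list and Appendix 9 the same instruction, and remove the reduction option because no lower dose exists. This is needed whichever bilirubin limit is chosen.

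The cost is two or three edited limits and one aligned instruction. No new assessment or change in sample size is needed.
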